2.4.1.3 Sensitivity Analysis of Primary Endpoint

A sensitivity analysis of the primary endpoint may be done looking at patients who received SMOF vs Intralipid as pre-randomization lipids. If less than ten patients received SMOF pre-randomization, then this sensitivity analysis will not be done.

2.4.2 Secondary Endpoints

All secondary endpoints will be performed on the FAS.

2.4.2.1 Liver Disease, Including Parenteral-Associated Liver Disease

2.4.2.2 Parenteral Nutrition-Associated Liver Disease (PNALD)

2.4.2.2.1 Derivation of PNALD

PNALD will be determined by a direct bilirubin measurement $\geq 2 \text{ mg/dL}$ at any timepoint in the study.

Time to PNALD will be derived using the start of treatment as the index date and the date of developing PNALD as the event date. It will be calculated for each patient as follows (standardized to the number of days):

Date of PNALD - Start Date of Treatment + 1

Patients will be censored at the time of their last lab value if they do not develop PNALD. Each patient will have their person time (or total exposure to potentially develop PNALD) calculated in "patient days" as:

> Date of first occurrence of PNALD or End Date of Treatment - Start Date of Treatment + 1

If a patient develops PNALD, then date of first occurrence of PNALD will be used. If a patient does not develop PNALD, then end date of treatment will be used. If a patient has more than 1 lab indicating PNALD, they will only be counted once at the date of their first instance. For incidence rate calculations, the total person time per group will be the sum of all individual patient's person time in that group standardized to 100 patient days:

Incidence Rate of PNALD =
$$\frac{Total \# with PNALD * 100}{\sum_{i=1}^{n} Person Time}$$

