- Genetic material will be obtained from buccal smears in all patients that consent to analysis of FADS1 and FADS2 polymorphisms
- From the subset of patients consenting to genetic analysis, the 10 patients (5 Intralipid and 5 Clinolipid) with the lowest levels of ARA at any point during the study and the 10 patients (5 Intralipid and 5 Clinolipid) with the highest levels of ARA at any point during the study will be selected for analysis of single nucleotide polymorphisms within FADS1 and FADS2 genes as the synthesis of ARA from linoleic acid (LA) requires both the delta-5 and delta-6 desaturase enzymes (coded for by FADS1 and FADS2).
- Distribution of the polymorphisms within FADS1 and FADS2 genes will be assessed in the context various FA findings as the synthesis of gamma-LA and ARA from LA (n-6 pathway) and the synthesis of stearidonic acid, eicosapentaenoic acid (EPA) and docosahexaenoic acid (DHA) from ALA (n-3 pathway) require both the delta-5 and delta-6 desaturase enzymes (coded for by FADS1 and FADS2 genes).

Secondary Endpoints:

The 3 secondary endpoints of the study include 1) the development of liver disease including PNALD; 2) the adequacy of nutritional intervention; and 3) the safety profiles including AEs, SAEs and AESIs.

- 1. Liver disease, including development of PNALD
- The risk of developing PNALD (as defined by direct bilirubin ≥2 mg/dL when no other etiology for liver dysfunction is present in patients receiving ILE) in pediatric patients will be summarized by treatment group as frequency and percentage, as well as time to developing PNALD using the Kaplan-Meier approach. Both incidence rate and proportion of PNALD will be computed for each treatment group.
- To assess the relationship of phytosterol, cholesterol and squalene blood levels and the development of PNALD, plasma phytosterol, cholesterol, and squalene levels will be summarized using descriptive statistics at baseline, at the end of study treatment, and as well as maximal values during the study period in each of the 2 treatment groups. In addition, the correlations

between plasma phytosterol levels and direct bilirubin will be assessed by computing a Pearson's correlation coefficient or a Spearman correlation coefficient.

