4.3 Exclusion Criteria

Patients who meet ANY of the following criteria will be excluded from the study:

- Patients who are not expected to survive hospitalization or with a severe critical unresponsive illness at time of initiation with foreseeable intercurrent events that could jeopardize the patient's participation in the study, as judged by the Investigator (e.g., unresponsive shock, sepsis, renal failure requiring dialysis, severe unresponsive metabolic acidosis, and/or severe unresponsive metabolic disorders);
- 2. Patients with a known hypersensitivity to lipid emulsion, egg or soybean proteins, or any of the active substances, excipients, or components of the container or who have a history of an adverse event due to ILE;
- 3. Patients with liver disease including cholestasis;
- 4. Patients with severe hyperlipidemia or severe disorders of lipid metabolism characterized by hypertriglyceridemia (triglyceride >400 mg/dL);
- 5. Patients who are unable to tolerate the necessary laboratory monitoring;
- 6. Patients who are enrolled in another clinical trial involving an investigational agent;
- 7. Patients with a known history of either severe hemorrhagic or severe hemolytic disease as judged by the investigator;
- 8. Premature infants born <24 weeks of gestation and patients ≥ 18 years;
- 9. Premature infants with a birth weight <750 g;
- 10. Patient requires or is expected to require propofol for sedation;
- 11. Patient, born to a symptomatic mother diagnosed with COVID-19 at time of birth or before birth;
- 12. Patient has received a diagnosis of COVID-19 (diagnosis <2 months prior and/or symptoms have not resolved);
- 13. Female patients who are pregnant. Note: All female patients ≥12 years of age must have a negative urine human chorionic gonadotropin (hCG) pregnancy test at screening. For female patients <12 years of age, a urine hCG test at screening will be performed at the discretion of the investigator based on childbearing potential.

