9.6.1 Liver Disease, Including Parenteral-Associated Liver Disease

9.6.1.1 Parenteral Nutrition-Associated Liver Disease

The risk of developing PNALD in pediatric patients by treatment will be summarized as frequency and percentage, as well as time to developing PNALD using the Kaplan-Meier approach. Both incidence rate and proportion of PNALD will be computed for each treatment group.

The incidence rate of PNALD will be computed as the number of patients who develop PNALD during the Study Treatment Period divided by the corresponding person time (i.e. "person-day" which is computed as "total number of patients" times "treatment exposure period [day]" in the corresponding treatment group), and reported as per 100 patient days. The proportion of PNALD will be computed as the number of patients who develop PNALD during the Study Treatment Period divided by the corresponding total number of patients.

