1.6.2 Secondary Endpoints

The secondary objectives in patients receiving either Clinolipid or Intralipid are to evaluate:

- The risk of developing liver disease including PNALD:
 - PNALD will be defined by direct bilirubin ≥2 mg/dL when no other etiology for liver dysfunction is present;
 - Hepatic integrity will be assessed by measuring plasma liver function tests: alkaline phosphatase (ALP), aspartate aminotransferase (AST), alanine aminotransferase (ALT), gamma-glutamyl transferase (GGT), and total and direct bilirubin;
 - Plasma main phytosterols (stigmasterol, campesterol, sitosterol), cholesterol and squalene levels will be assessed. Phytosterols levels will be correlated with the risk of developing PNALD.
- The adequacy of nutritional interventions:

- Prescribed and actual nutritional intakes (energy, protein, carbohydrates, and lipid) from both PN and enteral/oral nutrition will be collected and recorded on a daily basis and summarized on a daily basis during the first 2 weeks of treatment and on an approximately 15-day basis afterwards up to the end of study treatment in each of the treatment groups.
- Growth will be assessed and evaluated from baseline to end of study treatment on an approximately every 15-day basis using descriptive summary statistics for weight, and height/length (and head circumference in infant <1 year) in each of the treatment groups as follows:
 - Gain in weight (g/kg/day in infants <1 year of age, g/day in children and adolescents) and gain in length/height (mm/week in all) and head circumference (mm/week in infants <1 year);
 - Changes in the standard deviation score (SDS or z-score) from reference growth curves (Fenton growth curve for premature infants, World Health Organization (WHO) growth standards for infants and children ages 0 to 2 years, or Center for Disease Control (CDC) growth charts for children age ≥2 years).
- The safety profiles as evaluated by:
 - Adverse events (AEs)
 - Serious adverse events (SAEs)
 - Adverse events of special interest (AESIs)

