2.4.2.2.2 Analysis of PNALD

PNALD will be summarized at each visit as well as at the post-baseline maximal value (maximal being 'yes' to developing PNALD at any timepoint) by treatment group using frequencies and percentages.

If there are more than 5 cases of PNALD per arm, then time to develop PNALD will be analyzed using survival analysis approach (cumulative incidence), and the mean, standard error, Q1, median, Q3, minimum, and maximum for each treatment group will be displayed, where calculable. A cumulative incidence plot will also be produced. If there are less than 5 cases of PNALD in each treatment arm, then time to developing PNALD will be summarized descriptively by treatment group for all patients developing PNALD using n, mean, standard deviation, minimum, Q1, median, Q3, and maximum. If no events occur, then time to PNALD will not be calculated.

The incidence rate of PNALD will be computed and displayed per treatment group. The proportion of PNALD will be summarized per treatment group as the number of patients who develop PNALD divided by the corresponding total number of patients in each group.

A spaghetti plot consisting of direct bilirubin values over time will be produced with one line representing each patient, and different types of lines or symbols (e.g. solid and dashed) representing each treatment group. A bolded line will be added at y=2 to represent the bound for PNALD.

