3. CHANGES FROM ANALYSIS PLANNED IN PROTOCOL

There are no planned changes in analyses from the protocol.

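### The SAP derives PNALD from direct bilirubin alone and drops the condition that no other cause is present, so rises from any cause are reported as PNALD

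*SAP*

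**What the plan says.** The definition has two parts wherever it is given. SAP 1.6.2 reads "PNALD will be defined by direct bilirubin ≥2 mg/dL when no other etiology for liver dysfunction is present", and SAP 1.3, SAP 1.4.1 and Protocol 2.2 and 3.1 carry the same two conditions. The protocol synopsis, under its secondary endpoints, has PNALD "as defined by direct bilirubin ≥2 mg/dL when no other etiology for liver dysfunction is present in patients receiving ILE".

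The rule that would be programmed is in SAP 2.4.2.2.1: "PNALD will be determined by a direct bilirubin measurement" of at least 2 mg/dL, at any time in the study. The same section adds: "If a patient has more than 1 lab indicating PNALD, they will only be counted once at the date of their first instance". That date is the event date for time to PNALD and the end of the patient's person time for the incidence rate. SAP 2.4.2.2.2 then reports the frequency, percentage, incidence rate and time to PNALD by arm, again with no reference to etiology.

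SAP section 3 states: "There are no planned changes in analyses from the protocol". Protocol 9.6.1.1 describes the incidence rate as the "number of patients who develop PNALD during the Study Treatment Period divided by the corresponding person time" and does not restate the definition. Neither document says who decides whether another cause is present, when, or from which data.

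**The concern.** The etiology condition is what separates PNALD from any other rise in direct bilirubin. The secondary objective is liver disease including PNALD, so PNALD is meant to be the narrower, attributed outcome. Without the condition, the table headed as PNALD reports a laboratory event of any cause under the name of an attributed diagnosis.

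The entry criterion that excludes "Patients with liver disease including cholestasis" removes known disease at enrolment but not causes that arise later. Treatment can last up to 90 days. The recorded diagnoses requiring PN include necrotizing enterocolitis and sepsis (Protocol 6.3), and necrotizing enterocolitis and late-onset sepsis are collected on study (Protocol 7.2.3 and 7.2.4). Whether any of these explains a particular rise is a judgement on the individual case, and the SAP has no step at which to make it.

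The study is descriptive, with no formal testing (SAP 1.4.2), so no test result is at risk. The per-arm figures are themselves the result, and they should measure what their label says.

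**Working it through.** **1. Which conditions appear where**

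| Place | Direct bilirubin of 2 mg/dL or more | No other cause |
|---|---|---|
| Protocol synopsis, 2.2 and 3.1 | stated | stated |
| Protocol 9.6.1.1 | not restated | not restated |
| SAP 1.3, 1.4.1 and 1.6.2 | stated | stated |
| SAP 2.4.2.2.1 (derivation) | stated | absent |
| SAP 2.4.2.2.2 (analysis) | plot line only | absent |

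**2. What happens to an other-cause case under SAP 2.4.2.2.1**

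The first qualifying laboratory value makes the patient a case, supplies the event date and closes the person time. Under the full definition the same patient is not a case, is censored at the last laboratory value for time to PNALD, and contributes person time to the end of treatment.

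**3. Size per case, from the plan's own formulas**

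The documents give no PNALD figure to reproduce.

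- Input: 50 patients planned per arm (SAP 1.4.2). The proportion is cases divided by all patients in the group (SAP 2.4.2.2.2).
- Each other-cause case adds 1/50 = 2.0 percentage points. For an assumed 0 to 3 such cases in an arm, the excess is 0 to 6 points.
- Person time is event date (or end of treatment) minus start date plus 1. For a rise first seen on Day 15 in a patient treated to Day 90, the SAP rule gives 15 patient days and the full definition gives 90, a loss of 90 − 15 = 75. The incidence rate therefore rises through both its numerator and its denominator. The share of the arm's total person time depends on treatment durations, which the plan gives only as 7 to 90 days.

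**4. Illustration on assumed rates**

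Let p be the risk of PNALD under the full definition, and q the risk of an other-cause rise among the remaining patients. The SAP rule reports p + (1 − p)q. Neither rate is in the documents. With p = 4%:

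| Assumed q | Reported as PNALD | Share meeting the full definition | Chance of more than 5 cases in an arm of 50 |
|---|---|---|---|
| 0% | 4.0% | 100% | 1.4% |
| 4% | 0.04 + 0.96 × 0.04 = 7.8% | 51% | 19.6% |
| 8% | 0.04 + 0.96 × 0.08 = 11.7% | 34% | 53.7% |
| 12% | 0.04 + 0.96 × 0.12 = 15.5% | 26% | 80.9% |

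The last column matters because SAP 2.4.2.2.2 uses more than 5 cases per arm as the trigger for the survival analysis. Other-cause cases could therefore change the method as well as the count. With p = 12% and q of 4%, 8% and 12%, the reported figures are 15.5%, 19.0% and 22.6%, of which 77%, 63% and 53% meet the definition.

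**The case against.** The best defence is that SAP 1.6.2 defines the endpoint and 2.4.2.2.1 only names its laboratory trigger. This does not hold. The derivation makes no reference back, it treats the laboratory value itself as indicating PNALD, and a programmer who wanted to apply the full definition would find no procedure for doing so.

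Other points against have some force:

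- The plotting instruction "A bolded line will be added at y=2 to represent the bound for PNALD" proves little, since a line at 2 mg/dL on a direct bilirubin plot would be drawn under either definition. The finding does not need it.
- The number of affected patients is unknown and may be zero. The rates in the illustration are assumptions and do not support any claim about the actual excess.
- The harm is bounded. This is a secondary endpoint, and the laboratory-only rule can over-count PNALD but cannot hide a case. Direct bilirubin is also shown by visit, in shift tables and in listings, and adverse event listings carry alternate causality, so a reader could trace individual patients. That does not correct the headline percentage, rate or event times.
- Attribution after the fact is a judgement, and the data for it are incomplete. A raised bilirubin need not have an adverse event record (Protocol 6.13 and 6.13.6). The schedule of events marks neonatal morbidities only at end of treatment, although Protocol 7.2.3 also lists them at standard-of-care intervals. Their population is premature and low birth weight neonates in the schedule footnote, but premature infants only in Protocol 9.6.3 and SAP 2.5.2.1. These are reasons to keep the any-cause count visible beside the attributed one.

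**Conclusion.** The concern holds. SAP 2.4.2.2.1 contradicts the endpoint definition given in the protocol and in the SAP itself, and section 3 does not disclose it. The protocol shares part of the gap, because 9.6.1.1 does not restate the condition and no section says how it is to be judged.

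Confidence is high for the mismatch. Its effect on the results cannot be sized from the documents. What follows from the plan is 2.0 percentage points per other-cause case, assuming 50 patients per arm, and up to 75 patient days lost in the Day 15 example, which assumes treatment to Day 90. The SAP should be corrected, but no hypothesis test or planned between-arm contrast depends on it.

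**What to change.** Rewrite the event in SAP 2.4.2.2.1 as the first post-baseline direct bilirubin of 2 mg/dL or more during the Study Treatment Period, in a patient with no other cause of liver dysfunction. State that end-of-treatment samples drawn within the permitted ±2 days count.

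Judge etiology in a blinded review, before unblinding, of every patient who reaches the threshold. Write down beforehand the criteria and the data to be used: medical history, adverse events with alternate causality, and neonatal morbidities where recorded. Report direct bilirubin of 2 mg/dL or more from any cause as a supportive row.

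If the sponsor prefers the laboratory-only rule, label the outcome as direct bilirubin of 2 mg/dL or more, any cause, and declare the change in section 3. That removes the mislabelling but leaves the protocol's PNALD endpoint unreported, so it is a disclosed departure rather than an equivalent solution.

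As a minor clarification, state whether the exclusion of unscheduled results in SAP 2.1.2 applies to by-visit tables only, so that standard-of-care or unscheduled draws are not lost from the event derivation.

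The cost is SAP wording plus a review limited to flagged patients, which can run beside the blinded adverse event review already planned in SAP 2.5.1.1. The drawback is retrospective judgement, resting mainly on medical history and adverse events for patients without morbidity data; the any-cause row keeps the objective count in view. Relabelling needs wording only.

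### The SAP's PNALD event has no baseline condition and no post-baseline limit, so a patient already at direct bilirubin ≥2 mg/dL before study lipid can be counted as having developed PNALD

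*SAP*

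**What the plan says.** SAP 2.4.2.2.1 determines PNALD by a direct bilirubin of at least 2 mg/dL "at any timepoint in the study". Repeat values are handled by this rule: "If a patient has more than 1 lab indicating PNALD, they will only be counted once at the date of their first instance". On timing it says "Time to PNALD will be derived using the start of treatment as the index date", and the time is the event date minus the treatment start date plus 1. Person-time uses the same formula. It runs to the event for a case, and for everyone else "If a patient does not develop PNALD, then end date of treatment will be used".

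SAP 2.4.2.2.2 then says "PNALD will be summarized at each visit as well as at the post-baseline maximal value". It separately defines the proportion as "the number of patients who develop PNALD divided by the corresponding total number of patients in each group". SAP 2.4.2 puts all secondary endpoints on the FAS, and the only PNALD table in SAP Appendix 1 is an FAS table.

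Protocol 9.6.1.1 defines the rate as the "number of patients who develop PNALD during the Study Treatment Period divided by the corresponding person time", and it puts the same treatment-period limit on the proportion. SAP section 3 declares no change from the protocol's analyses.

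The relevant entry criterion in Protocol 4.3 excludes "Patients with liver disease including cholestasis", with no bilirubin figure attached.

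**The concern.** The endpoint is meant to describe liver disease that arises while the patient receives the randomised emulsion. The SAP's event rule does not say so. Hepatic tests are scheduled at Screening and at Baseline (Protocol Appendix 1), and SAP 2.1.2 displays both as visits, so values from before study lipid fall within the rule as written.

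Prior lipid exposure is foreseen. Protocol 5.3 allows parenteral nutrition with standard-of-care lipid to start before Screening, and SAP 2.4.1.3 plans for patients who received other lipids before randomisation. A raised direct bilirubin at entry would then be credited to the assigned emulsion.

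The parallel EFAD endpoint is better protected. SAP 2.4.1.1 limits the EFAD event to the period of study treatment, and Protocol 9.3 keeps infants with baseline EFAD out of treatment-emergent EFAD. PNALD, the first-listed secondary endpoint, has neither safeguard in the SAP, and neither document gives it a baseline rule.

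**Working it through.** Neither document states an expected PNALD rate or event count, and the sample size rests on feasibility, so there is no planned figure to reproduce. The check applies the SAP's formulas to a patient who is already at the threshold.

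**1. Time and person-time for a pre-dose value.** Formula (SAP 2.4.2.2.1): event date − start date + 1. Screening may begin up to 3 days before dosing (Protocol 7.1).

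| First qualifying value, relative to first dose | Days by the SAP formula |
|---|---|
| 3 days before | −3 + 1 = −2 |
| 2 days before | −2 + 1 = −1 |
| 1 day before | −1 + 1 = 0 |
| Same day, before dosing | 0 + 1 = 1 |

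The first three results are not valid survival times, yet in the rate each adds an event with zero or negative person-time. The fourth looks valid and would pass a range check.

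**2. Does the post-baseline maximum remove these patients?** There are two cases.

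- At ≥2 mg/dL at baseline and below 2 afterwards: the post-baseline maximum gives no, while the derivation in 2.4.2.2.1 gives yes. The two sections can disagree on the same patient.
- At ≥2 mg/dL at baseline and still there afterwards: both give yes. The patient counts as having developed PNALD and stays in the denominator.

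**3. Effect on the proportion.** Assumed, not in the documents: 50 patients in the arm, 3 incident cases, and 0, 1 or 2 prevalent cases. As written: (3 + prevalent)/50. Incident only: 3/(50 − prevalent).

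| Prevalent cases | As written | Incident only |
|---|---|---|
| 0 | 3/50 = 6% | 3/50 = 6% |
| 1 | 4/50 = 8% | 3/49 = 6.1% |
| 2 | 5/50 = 10% | 3/48 = 6.25% |

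**4. Effect on the rate.** Further assumptions: mean treatment of 20 days, incident cases at day 10, prevalent cases dated 1 day before start and so contributing 0 days.

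- 1 prevalent case: person-days = 46 × 20 + 3 × 10 = 950. As written, 4/950 = 0.421 per 100 patient-days; incident only, 3/950 = 0.316.
- 2 prevalent cases: person-days = 45 × 20 + 3 × 10 = 930. As written, 5/930 = 0.538; incident only, 3/930 = 0.323.

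A different mean duration changes the rates. When the prevalent cases contribute 0 days, the ratio of the two rates is simply the ratio of the event counts.

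**The case against.** The best defence is that the intended meaning can be recovered. SAP 2.4.2.2.2 uses the post-baseline maximum for the overall yes/no count and speaks of patients who develop PNALD. Protocol 9.6.1.1 sets the window, and the SAP declares no departure from it. So it is not settled that pre-treatment values will be counted, only that the derivation permits it. That stands, but it does not help with a patient who is at the threshold at baseline and stays there, since the post-baseline maximum is also yes.

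Second, eligibility should make such patients uncommon, because cholestasis is excluded and hepatic tests are scheduled at Screening. This also stands as a limit on size. But the criterion gives no bilirubin cut-off. SAP 1.5.1 itself lists enrolled patients with liver disease including cholestasis among deviations to consider for exclusion from the per-protocol set. In the FAS, on which PNALD is analysed, they remain.

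Third, the study is descriptive with no hypothesis tests, and the by-visit counts, the bilirubin plot and the listing would reveal a patient who began at or above 2 mg/dL. That is true, but the summary proportion and rate would still carry the error.

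A reader might also infer from the missing end date that events after treatment fall outside the rate's person-time. The documents do not support this. A case's person-time runs to its own event date, and end of treatment closes it only for non-cases. Scheduled samples stop within 2 days of the last treatment day (Protocol 7.2.4), and SAP 2.1.2 keeps unscheduled results out of the tables. A case first seen 2 days after the last dose contributes 7 + 2 = 9 days for a 7-day course, or 90 + 2 = 92 for a 90-day course.

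**Conclusion.** The point holds for values at Screening and Baseline. The SAP's event rule is looser than the protocol's and than the SAP's own EFAD rule, although no change is declared. Followed literally, it can count prevalent patients as having developed PNALD and can give them zero or negative times. The post-baseline maximum and the cholestasis exclusion narrow the problem without removing it.

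Each prevalent patient adds one event, or 2 percentage points (1/50), to an arm of 50. In the assumed example, 2 such patients turn 6.25% into 10%, and 1 turns 6.1% into 8%. The counts are illustrative: nothing in the documents predicts how many prevalent patients there will be, and with none the two rules agree. Because SAP 2.4.2.2.2 chooses its time-to-event method according to whether there are more or fewer than 5 cases per arm, one or two extra cases could also change the method used.

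It would go too far to say that pre-treatment values will certainly be reported as PNALD, or that post-treatment events corrupt the rate.

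**What to change.** In SAP 2.4.2.2.1, define incident PNALD as the first post-baseline direct bilirubin ≥2 mg/dL, through the end-of-treatment sample including its 2-day window. Restrict it to patients whose Screening value and baseline value (as defined in SAP 2.1.1) were both below 2 mg/dL.

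The limit should be post-baseline rather than after first dose. Protocol 7.2.1 and Appendix 1 allow baseline laboratory samples up to 24 hours after the first dose, and a raised value on that sample should not count as incident.

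Report patients at ≥2 mg/dL at Screening or Baseline in a separate row, outside the numerator and the at-risk denominator. Use the same window for the proportion, the rate, the person-time and the time to event.

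The cost is about two sentences in the SAP and a programming flag. The downside is that the at-risk denominator may shrink by a few patients.
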